6 SCHEDULE OF ASSESSMENTS

6.1 Informed Consent to Week 12 (Primary Endpoint)

Assessment	Informed Consent & Screening (Baseline)	Enrollment & Implant Procedure (≤ 30 d post-Informed Consent)	Post-Surgical Clearance ($14-21$ d post-Implant Procedure)	Day 0 (Randomization & Initiation of Stimulation) ($14-21$ d post-Implant Procedure)	Titration 1 (7 ± 2 d ²)	Titration 2 (14 ± 2 d ²)	Titration 3 (21 ± 2 d ²)	Week 4 (28 ± 3 d ²)	Week 8 (56 ± 5 d ²)	Week 12 (Primary Endpoint & One-way Crossover) (84 ± 7 d ²)
Informed consent	X*									
Vital signs	X*			X						X
Physical exam and medical history	X*									
Pregnancy test (childbearing female)	X*	X	X	X	X	X	X	X	X	
RA disease activity assessments ¹	X*			X				X	X	X
RA prior and current medication	X*									
Energizer fit test	X*									
SF-36 & EQ-5D-5L questionnaires	X			X				X	X	X
Blood collection (RF, ACPA, eGFR)	X									
Blood collection (CBC, biomarkers)	X			X				X	X	X
Hand MRI	X									X
12-lead ECG	X									X
X-ray cervical spine	X									
Surgical clearance	X		X							
Implant procedure in operating room		X								
Randomization				X						
Subject training on the use of Energizer				X						
Device check & dose titration				X	X	X	X			X ³
Device check & dose adjustment if needed								X	X	
Blinding assessment ⁴								X		X
Treatment decision for long-term follow-up										X
Device deficiency reporting		X	X	X	X	X	X	X	X	X
Adverse event reporting	X	X	X	X	X	X	X	X	X	X
Concomitant medication	X	X	X	X	X	X	X	X	X	X

Abbreviations: ACPA, anti-citrullinated protein antibodies; CBC, complete blood count; d, day; EGA, evaluator's global assessment; eGFR: estimated glomerular filtration rate; HAQ-DI, Health Assessment Questionnaire Disability Index; hsCRP, high-sensitivity C-reactive protein; MRI, magnetic resonance imaging; RA, rheumatoid arthritis; RF, rheumatoid factor; SGA, subject's global assessment; SJC, swollen joint count; TJC, tender joint count

* Screening assessments that must be conducted on the day of informed consent to determine subject's initial eligibility and baseline values for the primary and key secondary efficacy endpoints.

¹ RA disease activity assessments include: HAQ-DI, SGA, subject's pain assessment, TJC28, SJC28, EGA, and hsCRP. Subjects must have ≥ 4 TJC28 and ≥ 4 SJC28 at consent to be eligible.

² From Day 0 (randomization).

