6.2 Long-Term Follow-Up

Assessment	Titration 4 (91 ± 2d ²)	Titration 5 (98 ± 2d ²)	Titration 6 (105 ± 2d ²)	Week 24 (168 ± 7d ²)	Week 36 (252 ± 14d ²)	Week 48 (336 ± 14d ²)	Week 60 (420 ± 14d ²)	Week 72 (504 ± 14d ²)	Week 84 (588 ± 14d ²)	Week 96 (672 ± 14d ²)	Week 108 (756 ± 14d ²)	Week 120 (840 ± 14d ²)	Week 132 (924 ± 14d ²)	Week 144 (1,008 ± 14d ²)	Week 156 (1,092 ± 14d ²)	Week 168 (1,176 ± 14d ²)	Week 180 (1,260 ± 14d ²)	Week 192 (1,344 ± 14d ²)	Week 204 (1,428 ± 14d ²)	Week 216 (1,512 ± 14d ²)	Week 228 (1,596 ± 14d ²)	Week 240 (1,680 ± 14d ²)	Week 252 (1,764 ± 14d ²)	Week 264 (1,848 ± 14d ²) (End of Study)
Vital signs				X	X	X	X	X	X	X	X	X	X	X	X	X	X	X	X	X	X	X	X	
Pregnancy test (childbearing female)	X	X	X	X	X	X	X	X	X	X	X	X	X	X	X	X	X	X	X	X	X	X	X	
RA disease activity assessments ¹				X	X	X	X	X	X	X	X	X	X	X	X	X	X	X	X	X	X	X	X	
SF-36 & EQ-5D-5L questionnaires				X		X				X				X			X							
Satisfaction questionnaire				X																				
Blood collection (CBC)				X	X	X	X	X	X	X	X	X	X	X	X	X	X	X	X	X	X	X	X	
Blood collection (biomarkers)				X																				
Hand MRI				X																				
12-lead ECG				X		X				X				X			X							
Device check & dose titration	X ³	X ³	X ³																					
Device check & dose adjustment if needed				X	X	X	X	X	X	X	X	X	X	X	X	X	X	X	X	X	X	X	X	
Device deficiency reporting	X	X	X	X	X	X	X	X	X	X	X	X	X	X	X	X	X	X	X	X	X	X	X	
Adverse event reporting	X	X	X	X	X	X	X	X	X	X	X	X	X	X	X	X	X	X	X	X	X	X	X	
Concomitant medication	X	X	X	X	X	X	X	X	X	X	X	X	X	X	X	X	X	X	X	X	X	X	X	

Abbreviations: CBC, complete blood count; d, day; EGA, evaluator's global assessment; HAQ-DI, Health Assessment Questionnaire Disability Index; hsCRP, high-sensitivity C-reactive protein; MRI, magnetic resonance imaging; RA, rheumatoid arthritis; SGA, subject's global assessment; SJC, swollen joint count; TJC, tender joint count.

¹ RA disease activity assessments include: HAQ-DI, SGA, subject's pain assessment, TJC28, SJC28, EGA, and hsCRP. Subjects must have ≥ 4 TJC28 and ≥ 4 SJC28 at consent to be eligible.

² From Day 0 (randomization).

³ Dose titration is not performed if subject and Co-PI Rheumatologist decide that subject should not receive active stimulation in open-label, long-term follow-up period.

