May not be reproduced outside of SetPoint Medical without written permission from Document Control.

46 of 111

	
baseline to Week 12, 24, 48, 96, 144 and 192
 
 RAMRIS bone erosion, osteitis, synovitis, and CARLOS score change from baseline to Week 12 and 24 RAMRIS bone erosion progression (> 0.5) rate from baseline to Week 12 and 24 Change in plasma biomarker concentrations (e.g., IL-6, SAA, MMP3) 	
Safety		
To evaluate the safety of the SetPoint System	
Incidence of AEs and SAEs from informed consent to Week 264
 
Incidence of device malfunctions from Implant Procedure to Week 264
	
The incidence of treatment emergent AEs and SAEs that are more common in the treatment group compared to control is a standard measure of the safety. The incidence of device malfunction informs about the device reliability.

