15. Fibromyalgia that may confound outcome measures such as tender joint count, evaluator's global assessment, subject's global assessment, subject's pain, HAQ-DI, SF-36, or EQ-5D-5L

16. Known clinically significant cerebrovascular atherosclerotic disease including contralateral carotid artery disease (non-implanted side)
17. History of or pre-surgical X-ray that shows cervical spine disorder or instability that, in the investigator's opinion, would preclude safe endotracheal anesthesia or could be exacerbated by the implant procedure
18. Estimated glomerular filtration rate (eGFR) less than or equal to 50 mL/min/1.73 m² at Screening. eGFR eligibility must be confirmed prior to Screening hand MRI
19. History of left or right carotid surgery (e.g., carotid endarterectomy or stent)
20. History of unilateral or bilateral vagotomy
21. Partial or complete splenectomy
22. Recurrent vasovagal syncope episodes
23. Clinically significant cardiac rhythm disturbances, or ECG findings of atrioventricular block exceeding first degree, or cardiac conduction pathway abnormalities other than isolated right bundle branch block and/or isolated left anterior fascicle block on Screening ECG
24. Cancer within last 3 years, except fully resected basal or squamous skin cancer, fully resected cervical carcinoma in situ, or fully treated mammary ductal carcinoma in situ that has been in clinical remission for at least 3 years
25. Clinically significant esophageal dysfunction such as dysphagia, odynophagia, or esophagitis
26. History of or current, clinically significant vocal cord dysfunction, vocal cord polyps, or thyroid nodules.
27. Active and uncontrolled peptic ulcer disease
28. Implanted active medical devices (e.g., cardiac pacemakers, automatic implantable cardioverter-defibrillators, drug pumps), or likely need for implantation of such devices within 6 months
29. Uncontrolled asthma, chronic obstructive pulmonary disease, sleep apnea, or any other pulmonary disease such as interstitial lung disease causing clinically significant dyspnea
30. Limited life expectancy due to terminal disease
31. Hypersensitivity/allergy to MRI contrast agents and/or unable to perform MRI (e.g., claustrophobia)
32. Unable to use or wear Energizer
33. Requires treatment by any of the prohibited interventions (see Section 14.4)
34. Currently participating in another clinical research study with an investigational drug or medical device

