The remaining screening assessments can be completed on the day of informed consent or shortly after, depending on scheduling abilities:

- Concomitant medications
- SF-36 and EQ-5D-5L questionnaires
- Blood collection for RF, ACPA, eGFR, CBC and biomarkers (see Section 12.3)

Note: eGFR must be confirmed prior to screening hand MRI

- Hand MRI (see Section 12.4)
- Reporting of any AEs

Pre-surgical clearance must be completed by the Co-PI Surgeon prior to the scheduled implant procedure and entails:

- Review of the screening data collected by the rheumatologist investigator
- 12-lead ECG and any additional tests required for surgical or anesthesia clearance per hospital's standard of care
- Standard cervical spine X-ray, including anterior-posterior, lateral full flexion and extension, and odontoid views to ensure there are no degenerative or inflammatory changes observed in the cervical spine that would predict significant risk for atlanto-axial subluxation during neck extension required for endotracheal intubation prior to implantation (Krause and Matteson 2014). Cervical spine disorders or instability that would preclude safe endotracheal anesthesia will render the subject ineligible. The radiology report shall be filed with the subject's source documentation.
- An assessment of eligibility based on criteria associated with comorbidities or current status of physical fitness that would make the subject medically unfit for the implant procedure.

Based on all screening assessments, Co-PI Rheumatologist conducts a final eligibility evaluation:

- A subject must meet all the inclusion criteria and none of the exclusion criteria to be eligible. A subject not meeting all inclusion criteria or meeting any exclusion criterion will be classified as a screen failure and exited from the study. The reason(s) for screen failure will be documented.

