11.3 Enrollment and Implant Procedure

Subjects meeting final eligibility criteria and in whom the implant procedure is attempted are considered enrolled. The implant procedure shall occur within 30 days from informed consent. The implant procedure is an outpatient procedure taking place in an operating room under general anesthesia. The implant (MicroRegulator) and POD will be placed on the left cervical vagus nerve within the carotid sheath by surgeons trained and experienced in procedures involving implantation of VNS devices. The implant procedure must be performed according to SetPoint System Instructions for Use Surgeon Manual. All surgeons performing the implant procedure must have documented training prior to performing the first case. Upon completing the implant procedure, any AEs, device deficiencies and changes in concomitant medications will be recorded.

The pregnancy testing for female subjects of childbearing potential must be completed before initiation of the implant procedure (see Section **12.1**).

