12.3 Clinical Laboratory Tests

Blood samples will be collected at the site and sent to a central laboratory (ICON Laboratory Services) through Week 192. Analysis will include the following according to the schedule of assessments (see Section 6):

- RF
- ACPA
- eGFR
- CBC; and
- Inflammatory biomarkers (e.g., IL-6, SAA, MMP3).

The central laboratory will provide each site with sampling kits, shipping boxes and detailed instructions on blood sample collection, preparation and shipping.

Blood samples collected at Week 204 through Week 264 will be analyzed locally. The following analytes will be tested:

- Complete blood count (CBC), platelet count, differential count

All laboratory reports shall be reviewed by the site investigator and filed in the subject binder. In the event of a clinically significant abnormality, an adverse event shall be reported and labs shall be repeated and monitored at the investigator's discretion until resolved or considered medically stable.

Samples collected for surgical clearance shall be in accordance with the site's standard of care practices and analyzed locally. Testing may include:

- Platelet count, differential count
- Serum sodium, potassium, bicarbonate, chloride, magnesium, calcium, BUN, serum creatinine
- Urinalysis; and
- PT, PTT, INR.

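### eGFR is scheduled only at Screening, so these documents set no renal recheck before the Week 12 and Week 24 gadolinium doses

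*Protocol*

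**What the plan says.** Protocol 12.4 describes one contrast-enhanced hand MRI procedure, with images taken before and after gadolinium, and applies it at Screening, Week 12 and Week 24. It makes no exception for the later scans. A scan rejected for quality is repeated within 7 days.

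The renal condition is stated twice, each time for the first scan only. Exclusion 18 in 10.2 bars an eGFR of 50 mL/min/1.73 m² or lower and adds "eGFR eligibility must be confirmed prior to Screening hand MRI". Section 11.2.2 says "eGFR must be confirmed prior to screening hand MRI".

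In the schedule to Week 12 (6.1), the row "Blood collection (RF, ACPA, eGFR", together with its closing bracket, has a single mark, in the Screening column. Appendix A of the primary-analysis SAP shows the same. Bloods at Weeks 4, 8 and 12 are CBC, biomarkers and hsCRP (11.6.1, 12.2). The long-term schedule (6.2, and Appendix A of the long-term SAP) has a "Blood collection (CBC" row and a biomarker row, but no eGFR or creatinine row. Section 12.3 lists eGFR among the central-laboratory tests only as the schedule dictates. It names serum creatinine only as something local surgical-clearance testing may include.

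Section 16.5 links nephrogenic systemic fibrosis to gadolinium in renal failure and gives this as the reason for excluding subjects with low eGFR. Macrocyclic agents are required (14.4, 16.5). The later scans serve exploratory endpoints: "RAMRIS bone erosion, osteitis, synovitis, and CARLOS score change from baseline to Week 12 and 24" (Table 3).

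**The concern.** Making eGFR a condition of the Screening scan treats a recent kidney result as a precondition for contrast. By the protocol's own reasoning in 16.5, the same precondition is relevant to the second and third doses, yet neither has a scheduled check. The protocol also sets no maximum age for an eGFR result before contrast.

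The interval is long and not empty. It contains surgery under general anaesthesia, permitted perioperative changes to medication (14.2, 14.3), continued background csDMARD and, where used, NSAIDs. After Week 12, additional RA treatment may start at any time (14.5). The documents do not say that any of these lowers eGFR in this population, but they give no basis for assuming that it stays unchanged.

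What is at stake is subject safety during a study-specific procedure, not inference. Sample size, alpha and the primary and key secondary analyses do not depend on the MRI.

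**Working it through.** The plan states no figure to reproduce. The check is a count of scheduled tests against contrast doses, followed by the age of the Screening result at each later dose.

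**Count.** Scheduled contrast MRIs: 3 (Screening, Week 12, Week 24). Scheduled eGFRs: 1 (Screening). Doses with no scheduled recheck: 3 − 1 = 2.

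**Inputs** (Protocol 6.1, 6.2, 11.2.2, 11.3, 12.4), in days from Day 0:
- Implant no more than 30 days after consent. The eGFR draw may be on the consent day or shortly after.
- Day 0 is 14 to 21 days after implant.
- Week 12 is 84 ± 7, so 77 to 91. Week 24 is 168 ± 7, so 161 to 175.
- Repeat scan: up to 7 further days.

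**Age of the Screening eGFR** = (draw to implant) + (implant to Day 0) + (Day 0 to MRI), taking each MRI inside its visit window.

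| MRI | Youngest | Oldest | Oldest at a repeat scan |
|---|---|---|---|
| Week 12 | 0 + 14 + 77 = 91 | 30 + 21 + 91 = 142 | 142 + 7 = 149 |
| Week 24 | 0 + 14 + 161 = 175 | 30 + 21 + 175 = 226 | 226 + 7 = 233 |

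The youngest values assume a draw on the day of implant. That is unlikely. The usual route is "Blood samples will be collected at the site and sent to a central laboratory", and eligibility comes first: "Based on all screening assessments, Co-PI Rheumatologist conducts a final eligibility evaluation". Only then does 11.3 apply: "Subjects meeting final eligibility criteria and in whom the implant procedure is attempted are considered enrolled". But 19.1 lets eGFR be drawn and analysed locally under the COVID-19 contingency, so 91 and 175 should be read as the approximate lower ends that the windows allow, not as strict minima that every result must exceed.

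**Does surgical-clearance creatinine fill the gap?** Surgical clearance is marked in 6.1 at Screening and again at post-surgical clearance, which precedes Day 0. Even a creatinine taken at that second point would be at least 77 days old at the Week 12 MRI and 161 days old at the Week 24 MRI. It is also optional, follows site practice, and is not tied to either scan.

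**Age of the result under the proposed change.**
- Week 8 draw (56 ± 5, so 51 to 61) to Week 12 MRI: 77 − 61 = 16 shortest, 84 − 56 = 28 nominal, 91 − 51 = 40 longest.
- Week 24 draw to Week 24 MRI: at most 175 − 161 = 14.

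**Turnaround at Week 24.** Laboratory turnaround T is not stated, so 1, 3 and 7 days are assumed. The latest draw whose result returns by day 175 is 175 − T: day 174, 172 or 168. That covers 14, 12 or 8 of the 15 window days and leaves 1, 3 or 7 days on which a local test would be needed. At Week 8, any turnaround up to 16 days is in time.

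**The case against.** The strongest case against is that silence in the protocol is not evidence that contrast is given unchecked. Section 12.4 sends subjects to a facility selected and qualified for the procedure, working to a separate manual from the MRI central laboratory. Neither the manual nor the facility's practice is in these documents. A reader might infer that subjects receive gadolinium at Weeks 12 and 24 with no renal screening at all. The documents do not support that; they show only that the protocol schedules none. This part of the objection stands and limits the claim.

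The risk is also already reduced. Entry eGFR must exceed 50, uncontrolled hypertension and diabetes are excluded, and linear agents are prohibited. Adverse-event and medication review is listed before the MRI at both visits, and investigators may withdraw a subject on safety grounds (10.4). Section 16.5 ties the harm to renal failure, not to a modest fall from the entry level. These points stand as reasons to expect a small absolute risk. They do not supply a test: adverse-event review finds reported problems, and 16.5 justifies macrocyclic agents by brain deposition of gadolinium while keeping the eGFR exclusion as the separate control for nephrogenic systemic fibrosis.

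Finally, exclusion 18 is an eligibility criterion and properly looks only at Screening. That is correct, so the change belongs in the schedules and in 12.3 and 12.4, not in 10.2.

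**Conclusion.** The point holds as a gap in the schedule. Two of three planned contrast doses have no scheduled renal recheck, and the only scheduled result is about 91 to 142 days old at Week 12 and 175 to 226 days old at Week 24, or up to 149 and 233 days at a repeat scan. This assumes in-window visits. Confidence is high that the protocol and both SAPs contain no such check. It is not high that subjects are in practice unprotected, because that depends on the MRI manual and the facilities.

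Two further inferences should not be drawn. One is that cases of nephrogenic systemic fibrosis are to be expected: the documents give no rate of renal decline, so the number of subjects whose eGFR would fall to a level of concern cannot be derived. The other is that the efficacy conclusions are affected: RAMRIS is exploratory, and eGFR enters no SAP analysis. This is a worthwhile, low-cost improvement to safety monitoring and nothing more.

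**What to change.** Amend Protocol 6.1, 6.2, 12.3 and 12.4 as follows.

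- Add eGFR to the existing Week 8 and Week 24 draws.
- Require a post-Screening eGFR above the protocol's own entry limit (50 mL/min/1.73 m²) before contrast at Week 12 and at Week 24. Week 8 is the better draw for the Week 12 scan because crossover re-registration follows that MRI (11.6.1), and waiting for a Week 12 result would delay it.
- If the result is missing or not back in time, obtain a local eGFR, acquire the pre-contrast images only, or omit the exploratory MRI. State in 12.3 that a local eGFR for this purpose is not a deviation.
- State in 12.4 whether a repeat scan needs a new result.
- If the MRI manual already requires this check, a cross-reference in 12.4 is enough.

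No SAP analysis changes.

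The cost is a protocol and laboratory-manual amendment (with re-consent if the sponsor or IRB asks for it), one analyte at two draws, and local tests for some Week 24 visits depending on turnaround. Section 11.6.2 places the Week 24 MRI before the device check and dose adjustment, so these may wait for a result unless a local test is used. A few exploratory MRIs may be missed or done without contrast, and the MRI central laboratory would have to say which scores remain usable. The change narrows the gap rather than closing it: the Week 12 scan would still rest on a result up to 40 days old.

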10.3 Subject Status

Subjects will be classified as follows depending on their current status:

- *Consented*. After signing an IRB-approved informed consent form
- *Screen failure*. Subject not meeting all inclusion or meeting any exclusion criteria
- *Enrolled*. Subject meeting all inclusion and none of exclusion criteria in whom the implant procedure is attempted
- *Implanted*. Subject in whom the implant procedure is successfully completed
- *Randomized*. After being randomly assigned to either treatment or control group
- *Withdrawn*. Meeting one of the withdrawal conditions listed in Section **10.4**; or
- *Completed study*. After completing the study-required assessments at Week 264.

10.4 Subject Withdrawal

Enrolled subjects may be withdrawn for any of the following reasons:

- Subject death
- Concomitant disease or any pre-existing disease or condition that precludes subject's participation
- Subject voluntarily chooses not to participate further in the study
- Subject's non-compliance with study procedures
- Lost to follow-up, if a subject has missed a study visit, and 3 documented attempts to contact the subject have been unsuccessful. A subject who misses a study visit should be contacted by site personnel to determine the reason for the missed visit, which should be documented in the subject's study records. A subject who misses a study visit but attends a subsequent visit will no longer be considered lost to follow-up
- In the clinical investigator's opinion, a significant safety concern arises that requires subject discontinuation
- In the clinical investigator's opinion, it is not in the best interest of the subject to continue study participation
- In the study sponsor's or IRB's opinion, it is not in the best interest of subject to continue the study; or
- Study is terminated.

Clinical investigators should follow withdrawn subjects with ongoing AEs until resolution according to standard of care. Data collected up to the point of subject withdrawal or termination will be maintained in the study database and included in analyses as appropriate.

If, upon withdrawal, a subject wants or needs to have their implant permanently turned off and left in place, the implant will be decommissioned at the subject's last scheduled visit, or an unscheduled visit, if necessary. Implant decommissioning is described in Section **11.9**.

If, upon withdrawal, a subject wants or needs to have their implant removed, an explant procedure will be scheduled according to protocol Section **11.10**.

All enrolled subjects, including those withdrawn, will be accounted for and documented.

11 SUBJECT TREATMENT AND STUDY PROCEDURES

11.1 Pre-screening

During the pre-screening phase, clinical investigators or designees will perform an initial evaluation of potential candidates for study eligibility by reviewing their medical records to identify previously performed diagnostic measures, medical history, and labs in an effort to rule out subjects most likely ineligible for the study. Patients will be pre-screened as close to the date of consent and screening as is practicable. This will be included in the site training for the study. A log should be maintained to record limited details of those who were pre-screened, tracking the outcome of the screening (e.g., ineligible, potentially eligible but declined further study involvement, potentially eligible and attended a screening visit).

